1.4 Study design

This Phase II, open-label, non-randomized, multi-center cohort study will assess the efficacy (ORRs) and safety of olaparib monotherapy in relapsed ovarian cancer subjects who have received at least 1 prior line of platinum-based chemotherapy and have measurable disease, who have progressed at least 6 months after their last platinum-based chemotherapy, and who either carry a germline deleterious or suspected deleterious BRCAm, have a BRCAm in their tumor, have an HRD tumor accessed via the myChoice[®] HRD tumor test, or have wild type tumor type (BRCA and HRD).

The primary endpoint of the study is ORR. Secondary endpoints will include DoR, CA-125 response rate, DCR, PFS, TTAP, OS, HRRm gene panel related to clinical outcome, and safety assessments.

Approximately 450 subjects will be screened to identify up to approximately 300 subjects to be enrolled in 4 cohorts which will include at least 30 subjects in each. An individual cohort may continue enrollment up to 90 subjects (unless early stopping criteria are met) at which point the cohort will be closed to further enrollment. Once all 4 cohorts have at least 30 subjects (unless early stopping criteria are met), the study will be closed to further enrollment. All subjects enrolled will receive olaparib tablets 300 mg CC

n the active

[figure not shown]
treatment period of the study.

Subjects will continue treatment with olaparib tablets 300 mg CCI from from enrollment (Visit 2) until objective radiological disease progression as per RECIST v1.1 as assessed by the Investigator, or when they meet any discontinuation criteria (see Section 3.9). After documentation of disease progression, subjects will be followed for survival.

All subjects who enrolled and received at least 1 dose of olaparib will be followed for survival. Subjects will be contacted to assess survival status every 12 weeks following disease progression until death, withdrawal of consent, or study closure. Survival information may be

obtained via telephone contact with the subject, subject's family, or by contact with the subject's current physician.

See Figure 3 for a diagram of the study.

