2.2 Secondary objectives

Secondary Objectives:	Outcome Measures:
To determine the clinical effectiveness of olaparib treatment in each of 4 cohorts assessed using: • DoR, • CA-125 response rate, • DCR	• DoR, for those subjects with a confirmed response of CR or PR, response duration will be measured from the date of the measurement criteria for CR or PR are first met until the date of documented objective progression or death in the absence of disease progression.
 PFS, TTAP, OS, and 	• CA-125 response rate, defined as the percentage of subjects with a CA-125 response according to GCIG criteria divided by the number of subjects evaluable for CA-125 response.
HRRm gene panel status related to clinical outcome.	• DCR, defined as the percentage of subjects with a best overall response of confirmed CR or PR (at any time up to and including the defined analysis cut-off point) or who have demonstrated stable disease (SD) for at least 8 weeks from first dose, divided by the number of subjects in the efficacy analysis set.
	• PFS, defined as the time from the date of the first dose of olaparib to the earlier date of assessment of objective progression (per RECIST v1.1 criteria) or death by any cause in the absence of progression.
	• TTAP, defined as the time from the date of the first dose of olaparib to the earlier date of CA-125 progression (GCIG criteria) or RECIST v1.1 progression, or death by any cause in the absence of progression.
	• OS, defined as the time from the date of the first dose of olaparib to the date of death from any cause.
	• HRD status as per HRRm gene panel assessment (positive or negative) will be correlated with clinical outcome (ORR, defined above) for subjects enrolled in the 2 cohorts with BRCAwt (cohorts 3 and 4).

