4.2.4 Study Visit 7, Day 57, and every 4 weeks onwards

Subsequent on-treatment visits for the active treatment period will take place on Day 1 of a 4-week visit period up to 52 weeks (if not progressed and still on treatment), then on Day 1 of a 12-week visit period relative to date of enrollment until PD (RECIST v1.1). Subsequent on-treatment visits for subjects who remain on treatment post-progression should take place every 12 weeks. Tumor assessment visits will be performed at the end of every 8 weeks (± 1 week) up to 48 weeks, then every 12 weeks (± 1 week) relative to date of enrollment until PD (RECIST v1.1). Subjects will be contacted to assess for survival every 12 weeks following disease progression until death, withdrawal of consent, or study closure. See Section 4.4.

The following procedures will be performed at Visit 7, Day 57 (\pm 3 days) and every 4 weeks onward (i.e., Visit 8 [Day 85], Visit 9 [Day 113], etc.) through the active treatment period:

- Assess functional status using the ECOG performance status scale (see Appendix F);
- Obtain blood sample for hematology/clinical chemistry (see Section 5.2.1 and Table 8);
- Obtain blood sample for disease specific marker (CA-125) (see Section 5.2.1.4 and Table 8);
- Assess tumor (CT or MRI according to RECIST v1.1) (see Section 5.1.1);
- Note: The tumor assessments according to RECIST v1.1 will be performed every 8 weeks (± 1 week) from the first dose of study drug (Visit 2) for 48 weeks, and then every 12 weeks (± 1 week) (relative to the date of enrollment) thereafter until determined by the Investigator according to RECIST v1.1 criteria (including confirmatory RECIST scan).
- Assess and record concomitant medications including blood transfusions;
- Assess subject for adverse events (continuous from time of informed consent); and
- Dispense/return olaparib.

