8.4.3.3 Disease control rate

The DCR is defined as the percentage of subjects who have a best overall response of confirmed CR or PR or SD at ≥ 8 weeks divided by the number of subjects in the efficacy analysis set, prior to any PD event.

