8.4.3.4 Progression-free survival

Progression-free survival is defined as the time from the date of first dose of olaparib until the date of objective radiological disease progression (Investigator assessed via RECIST v1.1) or death (by any cause in the absence of disease progression) regardless of whether the subject withdraws from therapy or receives another anticancer therapy prior to disease progression. Subjects who have not progressed or died at the time of analysis will be censored at the time of the latest date of assessment from their last evaluable efficacy assessment. However, if the subject progresses or dies after 2 or more missed visits, the subject will be censored at the time of the latest evaluable assessment. Given the scheduled visit assessment scheme, 2 missing visits will equate to more than 18 weeks (or 26 weeks after 1 year) since the previous RECIST v1.1 assessment, allowing for early and late visits. If the subject has no evaluable visits or does not have a baseline assessment, they will be censored at Day 1 unless they die within 2 visits of baseline (18 weeks allowing for visit window).

The PFS time will always be derived based on scan/assessment dates and not visit dates. Assessments/scans contributing towards a particular visit may be performed on different dates. The following rules will be applied:

- Date of progression will be determined based on the earliest of the assessment/scan dates of the component that triggered the progression.
- When censoring a subject for PFS, the subject will be censored at the latest of the assessment/scan dates contributing to a particular overall visit assessment.

Overall visit assessments will be determined for each assessment (scheduled or unscheduled) and will contribute to the derivation of PFS.

Objective radiological progression is defined as at least a 20% increase in the sum of the diameters of the TLs (compared to previous minimum sum) and an absolute increase of > 5 mm, an overall non-TL assessment of progression, or a new lesion.

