Best response determination in studies where confirmation of CR or PR IS NOT required: Best response in these studies is defined as the best response across all time points (e.g., a subject who has SD at first assessment, PR at second assessment, and PD on last assessment has a best overall response of PR). When SD is believed to be best response, it must also meet the Clinical Study Protocol-specified minimum time from baseline. If the minimum time is not met when SD is otherwise the best time point response, the subject's best response depends on the subsequent assessments. For example, a subject who has SD at first assessment, PD at second, and does not meet minimum duration for SD, will have a best response of PD. The same subject lost to follow-up after the first SD assessment would be considered inevaluable.

Best response determination in trials where confirmation of complete or partial response IS required: Complete or partial responses may be claimed only if the criteria for each are met at a subsequent time point as specified in the Clinical Study Protocol. In this circumstance, the best overall response can be interpreted as in Table 15.

Overall response First time point	Overall response Subsequent time point	BEST overall response	
CR	CR	CR	
CR	PR	SD, PD or PR ^a	
CR	SD	SD provided minimum criteria for SD duration met, otherwise, PD	
CR	PD	SD provided minimum criteria for SD duration met, otherwise, PD	
CR	NE	SD provided minimum criteria for SD duration met, otherwise NE	
PR	CR	PR	
PR	PR	PR	
PR	SD	SD	
PR	PD	SD provided minimum criteria for SD duration met, otherwise, PD	
PR	NE	SD provided minimum criteria for SD duration met, otherwise NE	
NE	NE	NE	

Table 15	Best Overall Response When Confirmation of CR and PR is Required
----------	--

CR = complete response, PR = partial response, SD = stable disease, PD = progressive disease, and NE = inevaluable. a If a CR is truly met at first time point, then any disease seen at a subsequent time point, even disease meeting PR criteria relative to baseline, makes the disease PD at that point (since disease must have reappeared after CR). Best response would depend on whether minimum duration for SD was met. However, sometimes 'CR' may be claimed when subsequent scans suggest small lesions were likely still present and in fact the patient had PR, not CR at the first time point. Under these circumstances, the original CR should be changed to PR and the best response is PR.

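### The disease control rate credits stable disease only from 8 weeks after first dose, yet the first scan is on schedule from week 7, so some compliant early scans cannot establish it

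*Protocol*

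**What the plan says.** **Endpoint.** Section 8.4.3.3 counts as disease control a best response of "confirmed CR or PR or SD at ≥ 8 weeks divided by the number of subjects in the efficacy analysis set". Section 2.2 and the synopsis give the SD part as subjects "who have demonstrated stable disease (SD) for at least 8 weeks from first dose". None of the three places mentions the visit window.

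**Schedule.** Section 4.2.4 says that tumor assessments "will be performed every 8 weeks (± 1 week) from the first dose of study drug (Visit 2) for 48 weeks". Table 6 and section 5.1.1 give the same interval and window.

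**Best response.** Appendix G adds a minimum time for SD: "When SD is believed to be best response, it must also meet the Clinical Study Protocol-specified minimum time from baseline". Its example concerns someone "who has SD at first assessment, PD at second, and does not meet minimum duration for SD, will have a best response of PD". Table 15, for trials that require confirmation, grades an unconfirmed response followed by progression as "SD provided minimum criteria for SD duration met, otherwise, PD".

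**Comparison.** The progression-free survival (PFS) rule in section 8.4.3.4 uses the same schedule and does allow for early and late visits: "2 missing visits will equate to more than 18 weeks (or 26 weeks after 1 year").

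**The concern.** The threshold equals the nominal date of the first scan, while half of the permitted window lies before that date. Take two subjects who both have SD at the first scan and progression at the second. One is scanned 50 days after first dose and the other at 57 days. Both scans are on schedule, but only the second subject meets the 8-week condition. Their DCR status differs because of a scan date, not because of their disease.

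A late in-window scan creates no opposite error, so early and late scans do not cancel. DCR is a secondary endpoint reported with an exact 95% confidence interval in cohorts that may hold only 30 subjects, where one reclassified subject moves the estimate by 1/30 = 3.3 points.

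**Working it through.** All days below are days elapsed since first dose, so study Day 57 is 56 days.

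**1. The plan's own window arithmetic.** The protocol states no DCR figure. The nearest figure on the same schedule is the PFS limit for two missed visits, which is two intervals plus one week early and one week late:
- 2 × 8 + 1 + 1 = 18 weeks
- 2 × 12 + 1 + 1 = 26 weeks

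Both match section 8.4.3.4. The PFS rule therefore includes the ±1 week window. The DCR rule does not.

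**2. First-scan window against the threshold.**
- Window: 8 ± 1 weeks = 49 to 63 days, which is 15 calendar days.
- Threshold: 8 weeks = 56 days.
- On schedule but below the threshold: 49 to 55 days, which is 7 of 15 days, or 47%.

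Section 4.2.4 also lists the tumor assessment under Visit 7, Day 57 ± 3 days. That visit window is 53 to 59 days, and 3 of its 7 days (53, 54, 55) still fall below 56.

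**3. Who is affected.** The second scan is due at weeks 15 to 17.

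| First scan | Afterwards | DCR as written |
|---|---|---|
| SD at 49–55 days | SD or confirmed response at week 16 | controlled |
| SD at 49–55 days | progression, death or no further evaluable scan | not controlled |
| SD at 56–63 days | progression, death or no further evaluable scan | controlled |

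Only the middle row loses. Under Table 15, an unconfirmed response at an early scan followed by progression can lose in the same way. A subject with no evaluable scan after the early one stays in the denominator, because the efficacy analysis set needs only one dose and a baseline tumor assessment.

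**4. Size.** Loss in DCR = q × s, where
- q = share of first scans at 49–55 days;
- s = share of the cohort with SD or an unconfirmed response at the first scan and no later SD or confirmed response.

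The documents give neither value, so both are assumptions. The product also assumes that scan timing is unrelated to disease course. Loss in percentage points:

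| q | s = 5% | s = 10% | s = 20% | s = 30% |
|---|---|---|---|---|
| 10% | 0.5 | 1.0 | 2.0 | 3.0 |
| 25% | 1.25 | 2.5 | 5.0 | 7.5 |
| 47% (even spread over the window) | 2.3 | 4.7 | 9.3 | 14.0 |

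From the smallest to the largest cell this is about 0.2 to 4 subjects of 30, or 0.5 to 13 of 90. For scale, the exact 95% interval around an illustrative 21 of 30 (70%) runs from 51% to 85%.

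**5. The Appendix G clock.** Section 2.2 counts from first dose. Appendix G counts from baseline, and section 5.1.1 lets the baseline scan precede treatment by up to 28 days. If baseline means that scan, SD at 50 days is already 8 weeks from baseline when the baseline scan was 6 or more days before dosing (50 + 6 = 56). The same scan could then satisfy Appendix G and fail section 2.2.

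**The case against.** **The wording can be read more kindly.** Section 2.2 speaks of SD lasting 8 weeks from first dose. A subject with SD at 50 days and progression first seen at week 16 could be called stable past week 8. No section states this reading, and the section 8.4.3.3 wording, SD at 8 weeks or more, points the other way. If both readings are open, two programmers could get two DCRs from the same data, which also calls for a clarification.

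**The SAP may set a window.** The protocol promises a SAP with further detail, and it is not at hand. But the protocol does not leave this open: it fixes a number in three places. A SAP that used 7 weeks would depart from the stated endpoint.

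**Scans should fall near the nominal day.** Assessments are due at the end of each 8-week interval, Visit 7 is Day 57, and section 5.1.1 asks sites to keep closely to the schedule. This stands as a reason to treat the even-spread figure of 47% as an upper case. It helps only so far as scans fall on or after Day 57: an even spread over the ±3-day visit window would still put 3 of 7, or 43%, below the threshold.

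**Appendix G does not settle the example.** This stands in part. Its SD-then-progression example sits in the paragraph for trials without confirmation of response, and its minimum runs from baseline. A reader might infer that Table 15 applies the same 8 weeks from first dose, but the text does not say so. The DCR problem does not depend on this, because sections 2.2 and 8.4.3.3 set the threshold themselves.

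**Little turns on DCR.** This stands. The analyses are descriptive, and the primary endpoint and the futility rule use only complete and partial responses.

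**Conclusion.** The DCR threshold and the scan window do not fit together. SD seen at a compliant scan 49–55 days after first dose cannot count by itself, and the resulting error can only lower DCR. This is a stated rule, not a detail left open, and it deserves correction although no decision depends on it.

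Two stronger inferences are not supported:
- A reader might infer that all subjects with SD at an early scan are counted as failures. They are not: later SD or a confirmed response, for example at week 16, restores the subject to disease control.
- A reader might infer a definite shortfall of several points. The documents give neither q nor s. The range of 0.5 to 14 points rests on assumed values of 10–47% and 5–30%, and it is more likely toward the low end if sites scan on the nominal day.

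**What to change.** In the synopsis, section 2.2 and section 8.4.3.3, state that SD recorded at least 7 weeks (49 days, that is 8 weeks minus the 1-week window) after first dose qualifies as disease control. In Appendix G, state that the minimum SD duration, including in Table 15, is this same minimum counted from first dose.

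Every in-window first scan can then establish SD, so the loss from early compliant scans becomes zero. Scans before 49 days still would not qualify. The price is that a subject with SD at an early scan who progresses or dies before day 56 would count as controlled; that gap is at most one week.

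The cost is one sentence in each place and the matching line in the SAP. No scan, visit or data item changes.

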8.4.3.4 Progression-free survival

Progression-free survival is defined as the time from the date of first dose of olaparib until the date of objective radiological disease progression (Investigator assessed via RECIST v1.1) or death (by any cause in the absence of disease progression) regardless of whether the subject withdraws from therapy or receives another anticancer therapy prior to disease progression. Subjects who have not progressed or died at the time of analysis will be censored at the time of the latest date of assessment from their last evaluable efficacy assessment. However, if the subject progresses or dies after 2 or more missed visits, the subject will be censored at the time of the latest evaluable assessment. Given the scheduled visit assessment scheme, 2 missing visits will equate to more than 18 weeks (or 26 weeks after 1 year) since the previous RECIST v1.1 assessment, allowing for early and late visits. If the subject has no evaluable visits or does not have a baseline assessment, they will be censored at Day 1 unless they die within 2 visits of baseline (18 weeks allowing for visit window).

The PFS time will always be derived based on scan/assessment dates and not visit dates. Assessments/scans contributing towards a particular visit may be performed on different dates. The following rules will be applied:

- Date of progression will be determined based on the earliest of the assessment/scan dates of the component that triggered the progression.
- When censoring a subject for PFS, the subject will be censored at the latest of the assessment/scan dates contributing to a particular overall visit assessment.

Overall visit assessments will be determined for each assessment (scheduled or unscheduled) and will contribute to the derivation of PFS.

Objective radiological progression is defined as at least a 20% increase in the sum of the diameters of the TLs (compared to previous minimum sum) and an absolute increase of > 5 mm, an overall non-TL assessment of progression, or a new lesion.

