- k. Coagulation tests are only required if clinically indicated. For a list of all required laboratory tests, please refer to Section 5.2.1. All enrolled subjects will have safety blood samples taken weekly during the first month on treatment followed by monthly assessments until discontinuation of study treatment. Safety blood samples will be taken at the 30-day Follow-up Visit as well.
- 1. Women of childbearing potential must have a negative urine or serum pregnancy test within 28 days prior to starting treatment and a confirmatory test on Day 1 before initiating olaparib treatment; and at the timepoints shown in Table 6 during study treatment, and at the 30 day follow up visit. Pregnancy testing for women of childbearing potential should be conducted at regular intervals (eg, monthly). If results are positive, the subject is ineligible/must be discontinued from the study.
- m. Subjects with an unknown gBRCA status will have their blood and tumor tested with the myChoice[®] HRD and BRACAnalysis CDx[®] in parallel at pre-screening (if consented) or at screening, if not previously performed by Myriad during pre-screening.
- n. Subjects with known gBRCA status from the local laboratory must provide a blood and tumor sample at screening for confirmatory purposes. Their involvement in the study will not be affected by the result of the Myriad test.
- CA-125 will be tested at baseline and every month thereafter until objective disease progression, based on progressive serial elevation of serum CA-125 according to the modified GCIG criteria. Samples should be taken pre-dose at Visit 2.
- p. RECIST assessments will be performed using CT/MRI of the chest, abdomen, and pelvis, with other regions as clinically indicated for the assessment of disease, no more than 28 days prior to study treatment start and as close as possible to the start of study treatment. A CT examination with intravenous contrast media administration is the preferred method. An MRI should be used where CT is not feasible or it is medically contraindicated.

Date 10 October 2017

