5.1 Efficacy assessments

5.1.1 CT and MRI scans tumor assessments (RECIST v1.1)

The baseline tumor assessment will be performed no more than 28 days prior to study treatment start (Visit 2) and as close as possible to study treatment start. Following the

baseline tumor assessment, subsequent tumor assessments according to RECIST v1.1 should be performed at the end of every 8 weeks (\pm 1 week) from first dose of study drug (Visit 2) for 48 weeks and every 12 weeks (\pm 1 week) (relative to the date of enrollment) thereafter until PD. If an unscheduled assessment was performed and the subject has not progressed, every attempt should be made to perform the subsequent assessments at their scheduled visits. Subjects who are determined to have PD according to RECIST v1.1 criteria (including confirmatory RECIST scan) by the Investigator may have additional scans performed per the site's standard of care. All treatment decisions will be based on the Investigator's assessment of the scans.

A copy of all tumor assessment scans will be collected by an AstraZeneca Representative through disease progression.

All subjects should have RECIST assessments until documented evidence of objective radiological progression in accordance with RECIST v1.1, irrespective of treatment decisions (i.e., RECIST follow-up until progression even if a subject discontinues study treatment prior to progression and/or receives a subsequent therapy prior to progression).

At baseline, the imaging modalities used for RECIST assessment will be CT (MRI where CT is contraindicated) scans of the chest, abdomen, and pelvis, with other regions as clinically indicated for the assessment of disease. Follow-up CT or MRI assessments (per RECIST v1.1) will be by chest (in those subjects with disease in the chest or upper abdomen lymphadenopathy at baseline), abdomen, and pelvis, with any other regions imaged at baseline where disease was present. Any other sites at which new disease is suspected should also be appropriately imaged. The methods of assessment of tumor burden used at baseline must be used at each subsequent follow-up assessment. A CT examination with intravenous contrast media administration is the preferred method. An MRI should be used where CT is not feasible or it is medically contraindicated. For brain lesion assessment, MRI is the preferred method. Subjects must be followed-up until RECIST disease progression.

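### The 18-week equivalent of 2 missed visits in the PFS rule does not fit the first interval, where the previous assessment is a baseline scan taken up to 28 days before first dose

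*Protocol*

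**What the plan says.** Section 8.4.3.4 runs PFS from first dose and derives it from actual scan dates, not visit dates. Its missed-visit rule is that "if the subject progresses or dies after 2 or more missed visits, the subject will be censored at the time of the latest evaluable assessment". It then turns that count into time: "2 missing visits will equate to more than 18 weeks (or 26 weeks after 1 year) since the previous RECIST v1.1 assessment".

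On-study scans are tied to first dose. Under Section 4.2.4 they "will be performed every 8 weeks (± 1 week) from the first dose of study drug (Visit 2) for 48 weeks". The interval lengthens to 12 weeks beyond that point, with the same window. The baseline scan is tied to a window before first dose: the study plan in Section 4 asks for it "no more than 28 days prior to study treatment start and as close as possible to the start of study treatment". Section 5.1.1 treats it as a RECIST assessment: "At baseline, the imaging modalities used for RECIST assessment will be CT".

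One further sentence in Section 8.4.3.4 deals with the start of follow-up. It covers subjects who lack a baseline scan, or whose later visits yield nothing that can be evaluated. Its wording is: "they will be censored at Day 1 unless they die within 2 visits of baseline (18 weeks allowing for visit window").

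**The concern.** The threshold is counted from the previous RECIST assessment, but the visits it stands for are scheduled from first dose. Between two on-study scans the two clocks agree. In the first interval they differ by the age of the baseline scan.

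Take a subject with a baseline scan on Day -21, no evaluable week-8 scan, and progression at week 16. She has missed one visit, so the visit count makes her an event. Her gap is 3 + 16 = 19 weeks, so the 18-week equivalence makes her 2 visits missed and censors her. With a baseline scan 5 days before first dose the gap is 16.7 weeks and the same progression counts. Nothing about her disease or her missed visits differs.

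An affected subject loses an event at about week 16. Her latest evaluable assessment is the baseline scan, so read literally she is censored before the PFS clock starts, and in practice at time zero. Removing early failures in this way can only push the Kaplan-Meier PFS curve up.

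**Working it through.** **Inputs from the protocol.** Scans every 8 weeks ± 1 week from first dose to week 48, then every 12 weeks ± 1 week (Sections 4.2.4, 5.1.1). Baseline scan at most 28 days before first dose (Sections 4, 5.1.1). Threshold of more than 18 weeks, or 26 weeks after 1 year (Section 8.4.3.4).

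**Reproducing the plan's figures.** The largest gap with one missed scan between two on-study scans is 2 × interval + 1 week (earlier scan early) + 1 week (later scan late):
- 8-week phase: 2 × 8 + 1 + 1 = 18 weeks
- 12-week phase: 2 × 12 + 1 + 1 = 26 weeks

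Both stated figures are reproduced, so the rule was built for pairs of on-study scans.

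**First interval.** With the week-8 scan missing, gap = b + s, where b is the baseline lead time (0 to 4 weeks) and s is the week of the second scheduled scan (15 to 17).

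| Baseline lead | Scan at week 15 | Week 16 | Week 17 |
|---|---|---|---|
| 0 weeks | 15, event | 16, event | 17, event |
| 1 week | 16, event | 17, event | 18, event |
| 2 weeks | 17, event | 18, event | 19, censored |
| 3 weeks | 18, event | 19, censored | 20, censored |
| 4 weeks | 19, censored | 20, censored | 21, censored |

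Only one scan was missed in every cell. The maximum is 4 + 16 + 1 = 21 weeks. Counted from first dose, the maximum is 16 + 1 = 17 weeks, and the earliest in-window scan after two misses is at week 24 - 1 = 23. A limit of 18 weeks from first dose therefore separates one miss from two.

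**Share of one-miss progressions censored.** The protocol gives no distribution of baseline lead times, so this is an assumption. Take lead time in days and the week-16 scan (Days 105 to 119) as uniform, and count pairs that total more than 126 days:
- lead 1-14 days: 28 of 210 = 13%
- lead 15-28 days: 182 of 210 = 87%
- lead 1-28 days: 210 of 420 = 50%

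**Effect on 6-month PFS.** Assume exponential PFS with median m, a proportion p without an evaluable week-8 scan, and censoring at Day 1. The share of all subjects wrongly censored is c = p × F(16 weeks) × share. The last scheduled scan before 6 months is at week 24, so the estimate moves from S to about S / (1 - c), with S = S(24 weeks). In months, 16 weeks = 3.68 and 24 weeks = 5.52.
- m = 2: F = 1 - 0.5^(3.68/2) = 0.721; S = 0.5^(5.52/2) = 0.148
- m = 3: F = 0.573; S = 0.279
- m = 5: F = 0.400; S = 0.465

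With share 50%:
- m = 2, p = 5%: c = 1.8%, shift 0.3 points
- m = 2, p = 15%: c = 5.4%, shift 0.8 points
- m = 3, p = 15%: c = 4.3%, shift 1.25 points
- m = 5, p = 5%: c = 1.0%, shift 0.5 points
- m = 5, p = 15%: c = 3.0%, shift 1.4 points

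With share 13%, the shift runs from 0.07 points (m = 2, p = 5%) to 0.37 points (m = 5, p = 15%).

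**Early-death clause.** If baseline there means a scan on Day -28, 18 weeks ends at week 14 from first dose, before the week-16 window opens at week 15. If it means Day 1, it ends at week 18. The text does not say which.

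**The case against.** The best defence is that the operative rule is the visit count, and that the 18 weeks only explains it under a schedule that runs from first dose. On that reading a subject who missed one scan stays an event. The reading is available, and for that reason the fault is a conflict between two sentences rather than a rule that certainly censors. It does not settle the matter: the explanatory sentence names its own starting point, the previous RECIST assessment, the section works on actual scan dates, and nothing moves the count to first dose.

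A reader might infer that every early progression after one missed scan is censored. The documents do not support that. It needs a lead time above about 1 to 3 weeks, depending on when the second scan falls, and the protocol asks for the baseline scan as close as possible to treatment start. Section 8.4.3.4 also uses unscheduled assessments, so a late but evaluable first scan removes the problem.

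A reader might also infer that the bias is largest in the fastest-progressing cohort. More subjects are censored there, but the absolute shift in 6-month PFS is smallest: 0.8 points at a median of 2 months against 1.4 at 5 months, both with 15% missing. Nor are negative PFS times certain. The Day 1 floor for subjects with no evaluable visits shows the intended convention, although its wording does not reach a subject whose first evaluable on-study scan shows progression.

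Finally, PFS is secondary and untested (Section 8.5), and ORR is unaffected. A shift of 1.4 points is small beside simple binomial 95% half-widths of about 7-10 points at 90 subjects and 13-18 at 30. That stands, and it sets the severity.

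**Conclusion.** The point holds as an internal contradiction in a rule the protocol fixes itself; it is not a detail left to the statistical analysis plan. The 18-week figure is correct between on-study scans and up to 3 weeks too short when counted from the baseline scan. The consequence is limited to subjects without an evaluable week-8 scan whose baseline scan was old enough, and its direction is upward.

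Under the assumed 5-15% missing week-8 scans and median PFS of 2-5 months, the shift in 6-month PFS is about 0.1-0.4 points with baseline scans within 14 days of first dose, and about 0.3-1.4 points with scans uniform over 28 days. In the latter case 1.0-5.4% of subjects are affected, or about 1 to 5 in a cohort of 90. The missing-scan rate, the medians and the lead-time distributions are all assumptions; the documents give none of them. Severity: minor.

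**What to change.** Add one sentence to Section 8.4.3.4: where the only previous RECIST assessment is the baseline scan, the 18 weeks are counted from the date of first dose (Day 1), and any resulting censoring is at Day 1. In the early-death clause, define baseline as Day 1.

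This keeps the sponsor's threshold, makes the time rule agree with the visit count for on-schedule scans, and rules out negative PFS times. It needs no new data and should be settled before database lock. The cost is one sentence and one definition, carried into the analysis plan; reported PFS may become very slightly less favourable.
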